## 5.2 Samples

Samples collected for the protocol will be used for data analysis. Any remaining samples will be stored in the MTPB locked freezers according to subject consent sample designation. Samples of subjects who do not consent to future research use of samples will be destroyed at the end of the study. Approval of the IRB will be obtained prior to any research use of stored samples beyond the scope of this protocol. Only study investigators and participating research personnel will have access to the samples. The principal investigator will report to the IRB the loss or destruction of samples collected under this protocol.

#### 6 ADDITIONAL CONSIDERATIONS

#### 6.1 **Research with Investigational Drugs or Devices**

Review of the federal regulation, Title 21 (Food and Drugs) part 312 (Investigational New Drug Application [IND]), subpart A – General Provisions 312.2 (Applicability) was conducted, and it was determined that this protocol met all the exemptions for IND submission as described in 21 CFR 312.2(b)(1). It was determined that the route of study drug administration, dosage level, and use in the defined protocol patient population would not significantly increase the risk or decrease the acceptability of the risk associated with study drug use as planned in the protocol. Safety information on dexamethasone can be found in the package insert provided in Appendix 24.5. Dexamethasone irrigation is used by specialists for xerostomia, sialadenitis treatment or to decrease inflammation during oral surgical procedures.

#### 6.2 **Concomitant Medication Contingencies**

During the period of the study, subjects will not be allowed to use the following medications: human or murine antibodies, rituximab, warfarin, heparin, immunosuppressants (e.g., methotrexate, leflunomide, azathioprine, cyclophosphamide, systemic cyclosporine, systemic corticosteroids, and intra-articular corticosteroids), or any experimental drug. If it is necessary to prescribe one of these medications, the subject may participate in subsequent treatments, without repeating baseline MRI, NM Scan or Parotid Biopsy, after a washout of 3 months for immunosuppressants Additionally, subjects must refrain from the use of salivary stimulants within 24 hours prior to each study visit. If a subject enters the study on a stable dose of antimalarial drug or NSAID, the dose should not be increased during the study. All effort should be made to maintain stable dosing of other concomitant medications, including saliva substitutes.

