#### 3.2 Inclusion Criteria

- 1. Female gender and age 18 and greater..
- 2. Diagnosed with primary SS in Protocol 84-D-0056.
- Stimulated salivary flow of at least 0.01 mL/min from each parotid gland, using the standard operating procedure (SOP) for the National Institute of Dental and Craniofacial Research (NIDCR) Molecular Physiology and Therapeutics Branch (MPTB) Sjögren's Syndrome Clinic (Appendix 24.6).
- 4. Minor salivary gland biopsy with a focus score of ≥1 obtained 0 to 7 years prior to study enrollment. Biopsies from outside of the National Institutes of Health (NIH) must be reviewed by the NIH Pathology Department. An MSG biopsy will be required for the following situations:
  - a. The last biopsy was obtained before the use of rituximab.
  - b. The last biopsy was obtained before the use of immunosuppressants, biologics, or disease-modifying antirheumatic drugs for more than 3 months.
  - c. The last biopsy was obtained before the use of systemic corticosteroids (for more than 2 weeks or for shorter periods at doses of more than 0.5 mg/kg) or local parotid

corticosteroids. The use of topical or intra-articular/periarticular corticosteroids will not require a repeat biopsy.

- For women of childbearing potential, use of, or willingness to use, an effective method of birth control during the study. Effective methods include abstinence, history of hysterectomy, tubal ligation, intrauterine device, licensed hormonal methods, condoms, diaphragm, and cervical cap.
- 6. Ability to provide written informed consent prior to entry in the study.

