#### 4.3 Screening

Subjects who have been diagnosed with primary SS in Protocol 84-D-0056 will be eligible for participation. Subject consent will be obtained before any study activities or procedures. Screening will be conducted up to 12 weeks before Day 0 in two stages (Stage I & Stage II) to minimize procedures for subjects who do not meet initial salivary flow criteria. Multiple visits will be needed to complete the screening portion of the protocol.

Stage I screening assessments will be done within 6 weeks prior to Stage II and will include vital signs, medical and medication history, review of concomitant medications and evaluation of salivary flow. If salivary flow meets eligibility criteria the following additional Stage I procedures will be done: physical examination, pregnancy testing, routine clinical laboratory tests, and review of previous MSG biopsy. If the subject continues to meet eligibility for study participation according to the preceding assessments, she will undergo parotid saline irrigation and fill volume measurement. If an MSG biopsy has not been performed within 7 years of screening and an MSG biopsy needs to be performed, the saline irrigation and fill volume measurement will occur after the results of the MSG biopsy are obtained, as the final assessment of Screening Stage I.

Screening Stage II will be done within 6 weeks prior to Day 0 and will include vital signs, administration of the dry mouth questionnaire (Appendix 24.7), Sjogren's Disease Activity Index (Appendix 24.9), laboratory blood assessment for baseline values, magnetic resonance imaging, and technetium scan, and a parotid core needle biopsy. For the Screening Stage II, the pregnancy test must be within 24 hours before the technetium and MRI scans (for subjects of childbearing potential). A CBC with differential and platelets, PT, and PTT will be done within 7 days before each of the ultrasound-guided core needle parotid biopsies. All study visit procedures are detailed below in section 4.4 as well as a description of the approximate time to complete each procedure.

[figure not shown]
We will accept results of imaging procedures done elsewhere if completed within 3 months of enrollment (screen-stage 1 visit).

Subjects who randomize and receive one study treatment (Day 0) and take an excluded concomitant medication (immunosupressants) may re-screen. They will not have screening MRI, Technetium scan, or parotid biopsy procedures repeated.

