### 8 SUBJECT SAFETY MONITORING

All subjects will be monitored from the time of informed consent. Study procedures will be performed and monitored by licensed/certified NIH personnel. At each study visit, subjects will be evaluated for AEs and will be followed until resolution or stabilization of any AEs. All AEs will be graded according to a descriptive severity scale based on the National Institute of Allergy and Infectious Diseases (NIAID), Division of Acquired Immunodeficiency Syndrome Table for Grading the Severity of Adverse Events. The scale has been slightly modified for this protocol (Appendix 24.4 ). Pregnancy will be monitored throughout the study and subjects study participation will be stopped in the event of pregnancy. Emergency unblinding of a subject's

parotid gland randomization assignment will be allowed if the information is needed to treat a serious adverse event.

Serious adverse events will be reported to CROMS Product Safety group; each event will be reviewed by a CROMS medical monitor. The site's medically responsible Investigator will determine follow-up actions based on event intensity and whether it was expected and at least possibly related to study drug.

Subjects will be informed that they may withdraw or be excluded from the study at any time. The following conditions will require the discontinuation of study drug:

- Pregnancy
- New onset of a condition that requires treatment with any prohibited agent (Sections 3.3 and 6.2).
- Inability of study personnel to cannulate one or both parotid glands.
- Noncompliance with study procedures.
- Adverse event that would substantially increase the risk of continued participation.
- Investigator discretion.
- Violation of eligibility criteria.

Subjects who stop study treatment after receiving 1 of the two doses will be asked to complete the Day 56 assessments and the Safety Follow-up, excluding core needle biopsy of the parotid. Subjects who qualify for the study and who, prior to the first dose of study medication, elect to not receive treatment, will have the following assessments:

- Evaluation of AEs.
- Vital sign measurements (pulse rate, systolic and diastolic blood pressure, respiratory rate, and temperature).
- Laboratory tests if clinically indicated.

No additional data will be collected from subjects who withdraw completely from the study.

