#### 9.2 Secondary Outcome Measures

Secondary endpoints include the following:

- Change in focus score on parotid biopsy from Stage II screening to Day 56.
- Changes in salivary flow from Day 0 to study Days 14, 28, 42, and 56.
- Changes in assessments on the Patient Dry Mouth Questionnaire from Day 0 to study Days 14, 28, 42, and 56.
- Changes in assessments on the Sjögren's Disease Activity Index from Day 0 to study Days 14, 28, 42, and 56.
- Changes in other assessments of salivary function from baseline to study Day 56, including technetium scan of the salivary glands.
- Changes in laboratory measures of inflammation.
- Frequency of AEs related to treatment; location of the AE (body site, right or left), will be recorded and evaluated, as applicable.

Exploratory endpoints will be the changes in mechanistic endpoints from baseline to study Days 14, 28, 42, and 56.

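### Sections 8, 6.2 and 4.3 give different outcomes for a subject who needs a prohibited drug, and the return route measures focus-score change from a pre-drug biopsy

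*Protocol*

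**What the plan says.** **Section 8** introduces a list with the words "The following conditions will require the discontinuation of study drug". One entry is "New onset of a condition that requires treatment with any prohibited agent (Sections 3.3 and 6.2". A subject who stops after one of the two doses is asked back for the Day 56 assessments and the safety follow-up, but without the core needle biopsy. The section mentions no washout and no resumption.

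**Section 6.2** lists the prohibited drugs: antibodies, rituximab, warfarin, heparin and a group of immunosuppressants, ending "cyclophosphamide, systemic cyclosporine, systemic corticosteroids, and intra-articular corticosteroids), or any experimental drug". If one of them has to be prescribed, "the subject may participate in subsequent treatments, without repeating baseline MRI, NM Scan or Parotid Biopsy, after a washout of 3 months". The washout is stated for immunosuppressants only.

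**Section 4.3** says that subjects who were treated on Day 0 and then "take an excluded concomitant medication (immunosupressants) may re-screen". It adds: "They will not have screening MRI, Technetium scan, or parotid biopsy procedures repeated".

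**Section 9.2** defines the secondary endpoint as "Change in focus score on parotid biopsy from Stage II screening to Day 56". Under section 4.4.9 only the right parotid gland is biopsied. Section 9.2 also includes the technetium scan, from baseline to Day 56; it does not name MRI.

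**The concern.** There are two linked problems.

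The first is disposition. Section 8 cites section 6.2 by number and requires study drug to be discontinued. Section 6.2 itself, with section 4.3, provides for further treatment. The trial has a single site, but staff who work from different sections would handle the same subject differently, and the data would differ as well.

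The second is the baseline. If the subject returns, the parotid biopsy, technetium scan and MRI taken before the drug stay in force. The focus-score change then covers the first irrigation, the systemic drug, the washout and the later irrigation. For the scans, both glands are imaged, so a systemic effect can partly cancel between sides. For the biopsy it cannot, because there is no sample from the other gland. Focus score is the first-listed secondary endpoint and bears on whether irrigation reduces inflammation in the gland, so it matters what its change contains.

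**Working it through.** **Disposition.** The three sections set against the same event, a subject treated on Day 0 who then needs a prohibited immunosuppressant:

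| Section | Further study treatment | Day 56 parotid biopsy | Focus-score change |
|---|---|---|---|
| 8 | Study drug discontinued | Omitted | None |
| 6.2 | Allowed after 3 months' washout | Not excluded | From the pre-drug biopsy |
| 4.3 | May re-screen | Not excluded | From the pre-drug biopsy |

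For the other drugs on the section 6.2 list, the return sentence applies by its wording but gives no washout. At entry, section 3.3 has separate terms: 3 months for biologics, experimental therapy and immunosuppressants, 6 months for rituximab, and no current warfarin or heparin.

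**Interval from baseline biopsy to Day 56.** The plan states no figure for a returning subject, so there is nothing to reproduce. Inputs:

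- Biopsy to Day 0: at least 14 days (footnote to Table 4-1) and at most 6 weeks, or 42 days (section 4.3).
- Day 56 window: -3/+14 days, so 53 to 70 days (Table 4-1).
- Second dose at Day 28, so nominally 28 days before Day 56.
- Washout: 3 months = 3 × 365.25/12 = 91 days, or 13.0 weeks.
- Assumption for the minimum: the drug starts directly after the first Day 0 and its course is close to zero length.

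As planned:

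- Shortest: 14 + 53 = 67 days = 9.6 weeks.
- Longest: 42 + 70 = 112 days = 16.0 weeks.

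Returning, only the second dose remaining (biopsy + washout + 28 days):

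- 14 + 91 + 28 = 133 days = 19.0 weeks.
- With a biopsy 42 days before Day 0: 42 + 91 + 28 = 161 days = 23.0 weeks.

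Returning, Day 0 restarted (biopsy + washout + 56 days):

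- 14 + 91 + 56 = 161 days = 23.0 weeks. At the early edge of the window, 14 + 91 + 53 = 158 days = 22.6 weeks.
- With a biopsy 42 days before Day 0: 42 + 91 + 56 = 189 days = 27.0 weeks.

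The length of the drug course is added to each figure. Assumed courses of 2, 4 and 12 weeks turn the 19.0 weeks into 21.0, 23.0 and 31.0. Even the 19.0 weeks exceeds the planned maximum by 3 weeks. When treatment resumes, the retained biopsy is at least 14 + 91 = 105 days (15.0 weeks) old, against the 6-week limit for Stage II.

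**Weight of one returning subject.** The protocol states no balanced allocation of sides. If the 16 right glands split 8 and 8, one subject is 1/8 = 12.5% of a group mean. With groups of 6 and 10 it is 1/6 = 16.7% or 1/10 = 10%. A lasting shift of *d* focus units in that subject moves an 8-gland mean by *d*/8. The documents give no value for *d*.

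**The case against.** Several points on the other side are sound.

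- **Sections 6.2 and 4.3 can be read as one route.** Re-screening would ordinarily bring the section 3.3 exclusions back into play, and the 3-month washout matches the immunosuppressant exclusion there. This answers much of the washout point for immunosuppressants. It does not cover the wider wording of section 6.2, which extends to every listed drug.
- **Section 8 could mean a temporary stop.** It does not say so, and its follow-up without biopsy points to a permanent one.
- **The drug effect may be small or absent.** Section 1.1 cites a study in which six months of alternate-day prednisone did not improve gland histology or function. That is one regimen and not the whole prohibited list, but a large lasting effect cannot be presumed.
- **Handling of intercurrent drugs often belongs in the analysis plan.** True, but the rule not to repeat the procedures, the endpoint's baseline and the conflicting dispositions are all fixed in the protocol.

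A reader might also infer three stronger things that the documents do not support.

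The first is that the protocol's own rule invalidates the old parotid biopsy, since section 3.2 asks for a new biopsy where "The last biopsy was obtained before the use of systemic corticosteroids (for more than 2 weeks" or above a dose limit. That rule concerns the minor salivary gland and eligibility, has duration and dose thresholds, and exempts intra-articular steroids. It is an analogy only.

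The second is that the systemic drug would be credited to dexamethasone. Which treatment the right gland receives is randomised and blinded, and nothing suggests that side assignment influences who needs a prohibited drug. In expectation the comparison is not tilted either way.

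The third is that the primary endpoint is compromised. Salivary flow is not among the waived measurements, although the text does not say whether Day 0 is redone.

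**Conclusion.** The point holds in limited form. The contradiction between section 8 and sections 6.2 and 4.3 rests on the text alone and needs no assumption. The carried-over baseline is a stated rule. In a returning subject it makes the focus-score change span the whole systemic exposure and washout: at least about 19 weeks, or about 22 to 23 weeks if Day 0 is restarted, plus the drug course, against about 10 to 16 weeks planned. The lower figures assume a drug course of negligible length begun directly after Day 0, and a biopsy 14 days before it.

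The consequence is added noise and a distorted within-group change in a small secondary endpoint, not a bias towards dexamethasone. Its size cannot be computed, because the documents give neither the number of returning subjects nor the lasting effect of any listed drug. The correction is still worth making before data accrue, since the same event can otherwise yield different data.

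**What to change.** 1. Reconcile sections 4.3, 6.2 and 8 so that a given prohibited drug leads to one disposition. Which disposition is a clinical matter for the sponsor and investigator and is not judged here.
2. Reconcile the section 6.2 washout wording with the section 3.3 exclusions, so that it is clear which listed drugs the return route covers and on what terms.
3. If return is kept, say whether Day 0 is restarted or only the second dose remains.
4. If return is kept, state that biopsy-based change from the pre-drug baseline in returning subjects is left out of the focus-score change summary and listed separately, or shown as a sensitivity analysis.
5. For the same subjects, state that technetium and MRI changes are interpreted as between-gland differences and not as plain changes from baseline.

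The cost is amendment and analysis wording. No procedure is added or repeated. The downside is the loss of biopsy change from the few subjects, if any, who return.

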#### 7 RISKS AND DISCOMFORTS

#### 7.1 Assessments/Procedures with No Risks

The following assessments/procedures are deemed to have no risks and to cause no noteworthy discomfort: vital signs measurements, history and physical exam, urine collection, patient dry mouth questionnaire, and Sjögren's Disease Activity Index.

## 7.2 Collection of Saliva/Measurement of Salivary Flow Rate

There is no known risk associated with this procedure. Subjects may experience discomfort due to increased dryness caused by withholding salivary stimulants for 24 hours prior to saliva

CNS and NIDCR IRB Protocol Template (rev.9.21.11)Page 33 of 58

collection. There may be mild discomfort from positioning of mouth during collection. Citric acid (lemon juice) solution used to stimulate salivary flow may cause an unpleasant taste and mild discomfort in the salivary glands if the parotid duct is blocked and saliva cannot be expressed.

# 7.3 Parotid Fill Volume Determination and Saline Irrigation of Parotid Gland

Parotid fill volume will be measured before irrigations. Each subject will undergo 3 irrigations of each parotid gland, the first of which will use saline only. This procedure will involve placement of a catheter within Stensen's duct and filling of the duct with the appropriate solution, either dexamethasone or normal saline. The procedure may cause minor trauma to the parotid ducts and/or infection or inflammation of the parotid gland (sialadenitis). Other rare risks include perforation and/or scarring of the parotid duct(s) and damage to the facial nerve secondary to inflammation, infection, or scarring.

## 7.4 Intraductal Dexamethasone

Dexamethasone sodium phosphate is a synthetic adrenocorticosteroid indicated for a variety of disorders associated with inflammation. Like other glucocorticoids, it can cause profound and varied metabolic effects, as well as modify the body's immune responses to diverse stimuli. At equipotent anti-inflammatory doses, dexamethasone almost completely lacks the sodium-retaining property of hydrocortisone and closely related derivatives of hydrocortisone. Dexamethasone is contraindicated in persons with systemic fungal infections and in persons with hypersensitivity to any component of the formulation.

In this study, dexamethasone will be used topically in small doses within the parotid ducts; therefore, systemic exposure to the drug is expected to be extremely low. The dose (2 mg given twice 4 weeks apart) is within the range approved for intra-articular/intralesional use (0.2 to 6 mg administered once every 3 to 5 days to once every 2 to 3 weeks). Possible risks from local exposure in the mouth include irritation of the oral mucosa, temporary unpleasant taste, and increased risk of infection, allergic reaction, and pain. The risks associated with prolonged systemic exposure to dexamethasone (hypertension, diabetes, osteoporosis, glaucoma, increased risk of systemic infection, and adrenal insufficiency) are very unlikely to occur with this dosing regimen.

#### 7.5 Ultrasound-guided Parotid Gland Core Needle Biopsy

Subjects will undergo a core needle biopsy of the right parotid gland during the Screening Period and on Day 56. Ultrasound guidance will be used to localize the biopsy site within the gland, and local anesthetic will be administered to minimize pain during the procedure.

Several recent publications have described ultrasound-guided core needle biopsy of the parotid gland as a low-risk alternative to open surgical biopsy. Available published data indicate that the procedure is relatively simple and safe to perform and yields sufficient tissue for accurate pathologic diagnosis. The diagnostic accuracy (mainly for tumors) in 319 patients was 96% to 100%, with only 5 (1.6%) reported complications. Four of these complications were hematomas, most of which did not require any intervention. One patient with metastatic squamous cell carcinoma developed a parotid fistula after biopsy. The main risk of an open biopsy of the parotid is injury to the facial nerve (controlling motor function on the ipsilateral face); however, no such complication has been reported with ultrasound-guided core needle biopsy of the parotid, no SAEs were reported. One subject had an infected hematoma that responded promptly to antibiotics. The most common complaint was mild to moderate pain or discomfort at the site of the biopsy, which responded to simple analgesics. Other possible risks with the core needle biopsy are allergic reactions to the local anesthetic, bleeding at the biopsy site, and local infection; however, such events are rare.

Subjects in this study will be screened for a history of bleeding disorder and have a CBC with differential and platelets, PT, and PTT before each core needle biopsy. Any discomfort, pain, or swelling at the biopsy site will be treated with acetaminophen or more potent analgesics as needed. If facial nerve injury should occur, the subject will be referred to an appropriate subspecialist for care to minimize the damage. Subjects will be asked to sign a separate surgical consent form prior to the biopsy procedure.

